3.0 Specific Aims and Hypotheses

The purpose of this study is to evaluate the ability of RB shoes and AFOs to improve mobility, by alleviating pain and reducing joint motion when compared to a standard shoe. This study has three specific aims (SA):

SA 1: Compare the daily step count, **self-selected walking speed (SSWS)**, and self-reported outcomes from a set of questionnaires assessing pain and mobility before and after wearing a control shoe, RB shoe and a AFO. Each footwear condition will be worn over a three-week period (one-week acclimation, two-week trial period). This will indicate how subjects respond to these treatment conditions – what their pain levels are compared to baseline, how they self-report functional change, and from their step count, a quantitative measure of their mobility in the treatment footwear.

Hypothesis 1.1: For ankle OA subjects, the RB shoe and AFO will exhibit increased step count, self-selected walking speed, improve physical function, and reduced pain when compared to a control shoe.

Hypothesis 1.2: For ankle OA subjects, the AFO will increase step count, self-selected walking speed, improve physical function, and reduce pain more than the RB shoe or control shoe.

SA 2: Evaluate the effect of a control shoe, a RB shoe and a AFO on the front-to-back ROM of the foot and ankle. This will determine how these devices shield the ankle from motion – potentially protecting it, and if they impose abnormal motion on adjacent foot joints – potentially exposing them to additional wear and increasing their risk for long term OA development.

Hypothesis 2.1: For ankle OA subjects, the sagittal ROM of the talocalcaneal, talocrural, talonavicular, naviculocuneiform, and first cuneometatarsal joints will be less when wearing the AFO than the RB shoe, which will be less than OA subjects wearing the control shoe.

SA 3: Compare the ankle OA clinical and biomechanical outcome measures for the control shoe, RB shoe, and AFO to a healthy control group wearing control shoes. This will determine the difference in clinical and biomechanical outcomes related to the presence of OA.

Hypothesis 3.1: For ankle OA subjects, daily step count, self-selected walking speed, PROMIS physical function, and FAOS will be less, while the PROMIS pain interference, AOS-FAM, and numeric pain rating will be greater than the control subjects wearing the control shoes.

Hypothesis 3.2: For ankle OA subjects, the sagittal ROM of the talocalcaneal, talocrural, talonavicular, naviculocuneiform, and first cuneometatarsal joints when wearing RB shoes or AFOs will be less than the [sagittal] ROM of the control subjects wearing the control shoes.

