SA 3: Compare the ankle OA clinical and biomechanical outcome measures for the control shoe, RB shoe, and AFO to a healthy control group wearing control shoes. This will determine the difference in clinical and biomechanical outcomes related to the presence of OA.

Methods: We will enroll 100 participants with ankle OA and 50 control participants without lower limb pain. Three study groups will participate in this project. Study group 1 is a single day study and have images taken using our biplane fluoroscopy system. Study group 2 is a three month take home, and Study group 3 is a three month take home and will have images taken using our biplane fluoroscopy system. At visit-1 all participants will do baseline measures (questionnaires and functional assessments, including **SSWS**) and have a CT scan. During the initial visit, group 1 will participate in a biplane assessment. Participants in Study group 2 & 3 will be assigned to a randomly selected order of footwear (RB shoe, control shoe or an AFO). Each footwear condition will be worn for a three-week trial period at-home/in-community (one-week acclimation, two-weeks continuous wear). Participants will complete brief weekly pain assessments and wear a step counter. At visit-2 participants will do a pain rating, repeat the questionnaires and SSWS test, and group 3 will have images taken using our biplane fluoroscopy system. Participants will continue wearing the step-counter during a one week washout period. For the next three weeks, participants will repeat the at-

home/in-community procedures (step counter, weekly pain rating) and come to the VA to repeat the visit-2 procedures. The same process will be repeated for the third footwear condition.

List of Abbreviations

Provide a list of all abbreviations used in the protocol and their associated meanings.

AE - adverse event

AFO - ankle-foot orthosis

CT - computed tomography

mSv - millisievert

OA - osteoarthritis

RB - rocker bottom

ROM - range of motion

ROP - report of other problem

SAE - serious adverse event

SSWS - self-selected walking speed

UW/HMC - University of Washington/Harborview Medical Center

Contents

Protocol Title: Do Rocker Bottom Shoes and Ankle-Foot Orthoses Reduce Pain and Improve Mobility for Ankle Osteoarthritis Patients?..... 6

1.0 Key Study Personnel..... 6

2.0 Introduction..... 6

3.0 Specific Aims and Hypotheses..... 7

4.0 Resources and Personnel..... 8

5.0 Study Procedures..... 8

 5.1 Study Design..... 8

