5.4 Inclusion/Exclusion Criteria

Our targeted range for the total number of study completions is up to 150.

Inclusion Criteria:

Participants with ankle OA:

1. radiographic evidence of tibiotalar OA
2. age 18 years or older
3. able to stand and walk for about an hour (with breaks) and at least 15m (about 50ft) at a time without difficulty
4. minimum pain 3+/ 10

Control participants without OA:

1. age 18 years or older
2. able to stand and walk for about an hour (with breaks) and at least 15m (about 50ft) at a time without difficulty

Exclusion Criteria: all participants

1. subtalar joint arthritis
2. prior ankle joint replacement or fusion on the foot of interest, or recent (<1 year) surgical, neurological, rheumatologic, or lower limb musculoskeletal problem (e.g., current foot ulcer, severe hip/knee OA, terminal illness, etc.) that impairs an individual's ability to do the walking tests
3. current user of AFO or rocker bottom shoe and has either been prescribed by doctor or is not willing to stop using the device for three months
4. plans to undergo surgical treatment for ankle OA within three months
5. inability to walk unassisted during short, repeated walking trials
6. rheumatoid arthritis
7. inadequate cognitive or language function to consent or to participate
8. no phone number or stable mailing address
9. currently incarcerated
10. currently pregnant
11. open wounds on the foot or ankle
12. below- knee surgery in the past 60 days

Additional Exclusion Criteria, Controls only:

1. Ankle pain or ankle OA in addition to the above exclusionary criteria

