We will take video and photos of participants during portions of this study for documentation and use in research publications. All videos and photos will be anonymized (to avoid facial or voice identification) and tattoos and other distinguishing marks will be covered before images are captured or obscured during processing to protect the identity and privacy of our participants.

During study sessions, visitors and observers will not be allowed in the lab unless the participant agrees to their presence; the participant can change her/his mind at any time.

Study Footwear

Over the course of the study (one day or ~3 months) participants will be asked to wear up to three different footwear conditions: control shoes (a typical walking shoe, such as the New Balance 928), RB shoes (walking shoes with a front-to-back curved sole, such as the New Balance 928 with a rocker sole), and an orthotic device (such as an AFO, an ankle brace, such as the Toeoff[®] AFO) with control shoes. Participants will wear each footwear condition, in a randomized order. For all footwear conditions a fitbit zip may be clipped or taped to the shoe. This will record steps taken in the footwear. The fitbit will be synced during the VA visits and will only record number of steps. A separate account for each fitbit will be created and the account number will be recorded on the participant crosswalk. There will be no additional methods to link the data to the participant. Additional assessments on the initial day may include barefoot and own shoe as footwear conditions.

Screening /Eligibility Verification

Participants will have been preliminarily screened during recruitment, then during the first visit, after informed consent, we will make a final eligibility determination. This will include verifying that the information collected during recruitment is accurate and current.

If a participant cannot continue in the study, they will be compensated \$50 for the visit.

Demographic Data collection

Participants' age, sex, race/ethnicity and Veteran status will be recorded.

Anthropometrics

Participants' weight, waist circumference, and height will be measured.

Pain/health screening

Short survey which will include questions regarding trauma history in the lower limbs, joint replacements, OA, and pain throughout the body.

Functional Assessments

Self-selected Walking Speed (SSWS)

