For **Specific Aim 3**, hypotheses 3.1 and 3.2, the above model will be modified with the definition of the independent fixed effect, foot intervention, having an additional category representing the healthy control group. Post-hoc comparisons will focus on differences in mean step count, self-selected walking speed, physical function, pain or [sagittal plane] ROM between RB shoe or AFO and the healthy control subjects wearing the control shoes. Additional secondary analysis will be carried out using linear mixed effects regression to determine if pain (the dependent variable) correlates with [sagittal plane] ROM (the independent fixed effect, averaged over trial) and step count (the dependent variable) correlates with pain (the independent fixed effect) with study subject as a random effect in both sets of models. To determine if the mean differences in outcome by intervention (AFO vs. RB shoe) varies by OA severity, the regressions described above will be modified by adding two additional independent co-variates: OA severity and OA severity X intervention. The significance of the latter interaction term suggests that OA severity may influence outcome differences by intervention.

Power Analysis:

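### SA 3 ties OA-versus-healthy differences to OA status, but controls are neither balanced on age, sex or body size nor compared with adjustment for them

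*Combined protocol and SAP*

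**What the plan says.** Section 3.0 sets SA 3 as a comparison of OA participants, in each of the three footwear conditions, with healthy people in control shoes. It states the purpose as: "This will determine the difference in clinical and biomechanical outcomes related to the presence of OA". No limitation is attached.

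The Abstract gives the group sizes: "We will enroll 100 participants with ankle OA and 50 control participants without lower limb pain". In section 5.4 the two inclusion criteria for controls are "age 18 years or older" and "able to stand and walk for about an hour (with breaks) and at least 15m (about 50ft) at a time without difficulty". OA participants must meet both as well. The shared exclusions apply to controls, who have one further exclusion: "Ankle pain or ankle OA in addition to the above exclusionary criteria". OA participants also need radiographic tibiotalar OA and pain of at least 3 out of 10. Sections 5.2 and 5.4 contain no matching, quota or stratification of controls to the OA group.

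Under Statistical Methods in section 5.6, the SA 3 model is the SA 1 and SA 2 mixed model with the footwear factor "having an additional category representing the healthy control group". The post-hoc contrasts focus on OA participants in the RB shoe or AFO against healthy controls in control shoes. The only covariates added anywhere are OA severity and its interaction with intervention, for AFO versus RB shoe.

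The obvious covariates are in the data set. Section 5.5 says: "Participants' age, sex, race/ethnicity and Veteran status will be recorded". And: "Participants' weight, waist circumference, and height will be measured".

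**The concern.** Randomised footwear order protects SA 1 and SA 2, where each person serves as their own control and age, sex and body size cancel. It does nothing for SA 3, where the groups are different people who were not allocated at random. A subject random effect does not help either, because OA status varies only between persons.

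Step count, walking speed, physical function and joint ROM can plausibly vary with age, sex and body size whether or not a person has ankle OA. If the two groups differ on these, the planned model reports the resulting gap as an OA difference, and no planned analysis would show that it had happened. H3.1 and H3.2 are the only hypotheses under SA 3, so the whole aim rests on this comparison.

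H3.2 has a second problem. Its contrast sets OA participants in an RB shoe or AFO against healthy people in a control shoe, so disease and footwear change together. Covariate adjustment cannot separate them.

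**Working it through.** There is no plan figure to reproduce. The power analysis in section 5.6 (84%, 98% and 94%) concerns within-person footwear contrasts; the documents give no sample size, SD or effect for the SA 3 between-group comparison. The check is therefore a reading of the text followed by an illustration on assumed values.

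**Reading**

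- Design: the criteria in 5.4 restrict both groups on walking ability and comorbidity. None aligns the groups on age, sex or body size.
- Analysis: the model in 5.6 adds a fourth category and no demographic term.
- Data: 5.5 lists age, sex, weight, height and waist among the items collected.
- Pain: OA participants enter with pain of at least 3 out of 10 and controls with no ankle pain, so the pain contrasts are largely fixed by eligibility. The concern bears on steps, speed, physical function and ROM.

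**Illustration (assumed inputs)**

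Let the groups differ in mean age by *d* within-group SDs, and let age correlate *r* with the outcome within each group. With no true OA effect:

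- bias = *r* × *d*, in outcome SDs
- SE = √(1/n_OA + 1/n_control), one value per person, outcome SD = 1
- chance of a significant result at two-sided 5% = Φ(bias/SE − 1.96) + Φ(−bias/SE − 1.96)

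The assumed ranges are *d* = 0.5 to 1.0 and *r* = 0.2 to 0.4, so bias runs from 0.5 × 0.2 = 0.10 to 1.0 × 0.4 = 0.40.

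If everyone contributes, SE = √(1/100 + 1/50) = 0.173.

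- Low end: 0.10/0.173 = 0.577, giving Φ(−1.383) + Φ(−2.537) = 0.083 + 0.006 = 0.089.
- High end: 0.40/0.173 = 2.309, giving Φ(0.349) = 0.637, with the other tail negligible.

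For ROM the OA number is smaller. Section 5.5 confines biplane imaging to study groups 1 and 3, and the only ROM sample size in 5.6 is 30 enrolled with at least 25 remaining. Taking 25 OA participants, and assuming all 50 controls are imaged, SE = √(1/25 + 1/50) = 0.245.

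| Bias (SD) | Example *d* × *r* | 100 v 50 | 25 v 50 |
|---|---|---|---|
| 0.10 | 0.5 × 0.2 | 8.9% | 6.9% |
| 0.20 | 1.0 × 0.2 | 21.1% | 12.9% |
| 0.30 | 1.0 × 0.3 | 41.0% | 23.2% |
| 0.40 | 1.0 × 0.4 | 63.7% | 37.2% |

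The nominal rate is 5%. A smaller sample lowers the chance of a false claim but leaves the bias in the estimate unchanged.

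**Cost of adjusting for age**

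SE ratio = √(1 + q*d*²), where q = n_OA × n_control / N² = 100 × 50 / 150² = 0.222.

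- *d* = 0.5: √1.056 = 1.027, about 3% more.
- *d* = 1.0: √1.222 = 1.106, about 11% more.

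Both are before any gain from outcome variance that age explains.

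**The case against.** Several points on the other side are sound.

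- A reader might infer that the controls are simply any adults. They are not: they meet the same walking criterion and shared exclusions as the OA group and must be free of ankle pain and OA. This narrows the comparison but does not balance age, sex or body size.
- A reader might infer that controls will be younger or leaner, so that the bias exaggerates OA. The documents do not support a direction. Section 2.0 describes ankle OA as mostly post-traumatic and as affecting younger people than hip or knee arthritis does. Flyers, advertisements and the centre registry are not reserved for controls.
- Larger error rates can be produced: a 1.5 SD gap with a correlation of 0.4 gives 0.6 SD and 93% at 100 v 50. That needs both extremes at once and the full sample for every outcome. Nothing in the documents supports the first, and biplane imaging in only two study groups argues against the second for ROM. Step counts over take-home wear cannot come from a one-day visit either, so their OA number may also be below 100.
- The plan's wording is associational and does not claim causation. That is fair, but an unadjusted difference that mixes age and sex with disease is still a poor measure of what is linked to OA.
- BMI is a debatable adjuster. If painful OA limits activity and raises weight, adjusting for BMI could remove part of the difference sought. This stands and shapes the fix.
- The study's main purpose is the footwear comparison, and SA 1 and SA 2 are untouched. This limits the weight of the point but does not remove it.

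**Conclusion.** The point holds for SA 3 only. As planned, the step count, walking speed, physical function and ROM contrasts between OA participants and healthy controls can carry demographic differences that neither the design nor the model addresses. The pain contrasts are little affected.

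The omission is plain from the text. The size and direction of bias are not, because no group distributions are given. The range of about 9% to 64% false significance rests on an assumed age gap of 0.5 to 1.0 SD, an assumed correlation of 0.2 to 0.4, and all 100 and 50 participants contributing. With 25 OA participants and 50 controls, the corresponding range for ROM is about 7% to 37%.

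Separately, the H3.2 contrast cannot isolate OA even after adjustment, because footwear differs too. The contrast with both groups in control shoes does isolate OA status. It falls within SA 3 as worded but is not among the post-hoc contrasts on which 5.6 focuses.

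**What to change.** In section 5.6:

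1. Add age and sex as fixed effects in the SA 3 models for H3.1 and H3.2, and make the adjusted contrast the main reported result.
2. Show adjustment for BMI, computed from the height and weight already collected, as a sensitivity analysis, since BMI may partly result from OA.
3. Report group balance on age, sex and BMI.
4. Name the contrast of OA in control shoes against healthy in control shoes as the one that addresses OA status. Describe the RB shoe and AFO contrasts with healthy controls as differing in both disease and footwear.

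In section 3.0, word the SA 3 result as an association. Frequency matching on age and sex for controls still to be enrolled is a useful option but not essential.

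The cost is two covariates that are already collected and a small rise in SE, about 3% to 11% for an age imbalance of 0.5 to 1.0 SD. Optional matching may slow control recruitment slightly. SA 1 and SA 2 need no change.

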4.0 Resources and Personnel

Data collection procedures for this study will be conducted at the VA Puget Sound in Seattle, WA. See Study Staff Sheet attachment for listing of personnel, ability to obtain consent, and access to PHI.

Under the supervision of the PI, designated study staff will be responsible for conducting recruitment, consent and scheduling study procedures. The PI, Investigators, and/or Research Engineers and assistants will conduct procedures with participants. The PI, Investigators, and the Biostatistician will be primarily responsible for data analysis and interpretation; Research Engineers and assistants may also assist with this. Under the supervision of the PI, the Program Coordinator is responsible for IRB related matters.

5.0 Study Procedures

5.1 Study Design

Participants in this research study will be men and women, age 18 and over, who can walk without difficulty for about an hour. People with and without ankle OA, will be enrolled. Targeted enrollment by ankle OA status is listed in the table below. Vulnerable populations will not be specifically targeted for enrollment. See inclusion/exclusion criteria below in section 5.4.

Study Groups	Total: 150
Controls, no ankle OA	50
People with Ankle OA	100

See section 5.5 below for data collection procedures and risk management.

5.2 Recruitment Methods and Initial Screening

Up to 3000 individuals may be approached during recruitment and enrollment procedures. Please note that all references in this section to in-person contact/initial-screening will follow the *Screening Script* attachment, all references to approach letters and postcards refer to the *Recruitment Letter* attachment.

Recruitment activities at the VA

Medical Record/Database: Letter/Phone/In-person (Seattle and American Lake)

Designated research staff will screen relevant clinic lists in CPRS to identify potential participants with a qualifying ankle OA diagnosis. After review, designated staff will go to the clinic or contact providers on the phone or on VA encrypted email to ask if a patient might be a good fit for the study. If the clinician agrees that the study may be a good fit for a patient, during an appointment the clinician will inform patients of the availability of the study and ask if they are interested in speaking with designated study staff; patients will be given a chance to opt out. For patients who are interested, designated study staff will speak to potential participants directly and/or use CPRS to obtain potential participants' contact information (i.e., name, address, telephone number). For potential participants who learned about the study in person and were introduced to us but may not have time to complete the eligibility screening, designated study staff may give them a flyer and/or business card, and make a follow-up approach phone call, arrange a time to meet later in-person, and/or send an approach letter to them. If potential participants are unable to meet with designated study staff in-person, then we will send an approach letter.

We may also search CPRS and the Corporate Data Warehouse (CDW) to identify individuals with a qualifying diagnosis and mail them the approach letter.

If potential participants have not spoken with us within 14 days of the first call and/or mailing the approach letter, designated study staff will contact them by phone up to two more times (three times total) about this study. The approach letter will also include an "opt out" postcard. The opt-out postcard will have a unique study recruitment identification code, e.g., "RBS-AFOd1", "RBS-AFOd2". If an individual returns the postcard to opt out they will not be approached about this study again.

Clinician Referral

Designated staff will inform providers working in relevant clinics about the study and inclusion/exclusion criteria, so they can refer potential participants to contact the study team. Flyers and business cards may be provided to clinicians (or their support staff) to give to patients that are interested in learning about the study. Clinicians may also provide us (via VA encrypted email/in-person/on the phone) with the names of patients that they are aware of who may be a good fit for the study and we will look up their contact information to send an approach letter. If a clinician informs patients about the study and the patient agrees to be contacted about it, the clinician may provide us with the patient's name (via encrypted email/in-person/on the phone). We will look up the patient's contact information in CPRS and make an approach call (in this instance – we will obtain printable documentation from the clinician, via encrypted email or a note in the medical record, that the patient agreed to be contacted on the phone).

Print/Text/Online/Flyers/Newsletter

Flyers may be posted in designated areas at the VA Puget Sound (Seattle and American Lake) on the CCTV system and in publicly accessible locations in the community (e.g., public libraries, community centers, coffee shops). The flyers may also be re-sized to be used in print publications or as a complete image in online ads. We may post classified ads in print and online publications. We may also post the classified ad text to our Center's webpage. We may also post recruitment information in our center newsletter.

VA Puget Sound Center Registry: Letter/Phone

Designated study staff may also identify potential participants using the VA Center for Limb Loss Prevention and Prosthetic Engineering Subject Registry (PI: [name], #00433). The Registry contains contact information for participants who were screened for and/or participated in previous studies with our research group and consented to be contacted (via phone call and/or letter) for future studies. Designated study staff may make an approach phone call and/or send an approach letter to potential participants asking whether they are interested in the study. If potential participants have not spoken with us within 14 days of the first call and/or of the mailing the approach letter, designated study staff will contact them by phone up to two more times. The approach letter will also include an “opt out” postcard. The opt-out postcard will have a unique study recruitment identification code, e.g., RBS-AFOd1”, “RBS-AFOd2. If an individual returns the postcard to opt out they will not be approached about this study again. Designated study staff may also speak with these potential participants in-person if they have an upcoming clinic visit.

Eligibility Screening

Interested individuals will be screened for eligibility in-person or over the phone.

Recruitment Activities at UW/Harborview

A confidentiality agreement will be obtained for this activity. The UW is engaged in all aspects of this study. Also, we spoke with [name] at UW HSD and confirmed that [name] is not engaged as a UW agent for the purposes of this study or its recruitment activities.

Medical Record/Database: Letter/Phone/In-person (UW/Harborview)

Designated study staff will screen relevant UW/Harborview clinic lists, appointment calendars and patient medical records to identify potential participants with a qualifying ankle OA diagnosis. Study staff may also attend clinic at these facilities to identify and/or contact potential participants. Study staff will discuss with the clinician(s) (in-person or on the phone) any patients that might be appropriate candidates. If the clinician agrees that the study may be a good fit for a patient, the clinician will inform patients of the availability of the study and ask the patient if she/he is interested in speaking with study staff. For interested patients, study staff will speak to them directly to tell them more about the study, give them a study flyer, business card, and/or request their permission to screen them for initial eligibility (via the VA IRB approved screening script) and provide this information to the VA. If VA staff are not available in the clinic, the clinician or their support staff may provide the study flyer and/or VA research coordinator’s business card.

If potential participants are screened in person, study staff will label the noted responses with an id code and no HIPAA identifiers or sensitive health information will be noted on the form. Study staff will transport the forms to the VA for storage. Study staff will use their VA remote access to add PHI to the screening log that is maintained on the VA server, or they will call other approved staff to provide the PHI, and the information will be added to the VA screening log.

For potential participants who learned about the study in person and were introduced to us but may not have time to complete the eligibility screening, staff may give them a flyer and/or business card, look up their contact information to make a follow-up approach phone call, arrange a time to meet later in-person, and/or send an approach letter to them. If potential participants are unable to meet

designated study staff in-person, then we will send an approach letter (the VA IRB approved letter with VA contact information would be sent per the process described above).

Staff may also search/access UW medical records to identify individuals with a qualifying ankle OA diagnosis, obtain their contact information (i.e., name, address, telephone number) and mail them the approach letter.

Clinician Referral

Designated staff will inform providers working in relevant clinics about the study and inclusion/exclusion criteria, so they can refer potential participants to contact the study team. Flyers and business cards may be provided to clinicians (or their support staff) to give to patients that are interested in learning about the study. Clinicians may also provide us (via in-person/on the phone) with the names of patients that they are aware of who may be a good fit for the study and we will look up their contact information to send an approach letter.

For potential participants who were initially contacted via letter and/or in-person but have not yet completed the initial screening, study staff may provide the potential participants' contact information and limited pre-screening criteria over the phone to other study staff at the VA who will enter it into the screening log for tracking and follow up. This information may also be added (via VA remote access) to the screening log maintained on the VA server. Study staff will follow up with potential participants based on the VA approved protocol.

